9.3.2 Peripheral blood lymphocyte phenotypes

Lymphocyte subsets (CD3, CD4, CD8, CD19, and CD56) will be analyzed according to absolute cell numbers per microliter of whole blood, percent representation among all lymphocytes, and co-expression of the activation markers CD25, HLA-DR, and CD45RO using automated flow cytometric techniques at the Flow Cytometry Core Laboratory, Robert H Lurie Cancer Center of Northwestern University under the supervision of [name].

9.4 Specimen Banking

Patient samples collected for this study will be retained at the Northwestern University Biorepository. Specimens will be stored indefinitely or until they are used up. If future use is denied or withdrawn by the patient, best efforts will be made to stop any additional studies and to destroy the specimens.

[name] will be responsible for reviewing and approving requests for clinical specimen from potential research collaborators outside of Northwestern University. Collaborators will be required to complete an agreement (a Material Transfer Agreement or recharge agreement) that states specimens will only be released for use in disclosed research. Any data obtained from the use of clinical specimen will be the property of Northwestern University for publication and any licensing agreement will be strictly adhered to.

The following information obtained from the subject's medical record may be provided to research collaborators when specimens are made available:

- Diagnosis
- Collection time in relation to study treatment
- Clinical outcome – if available
- Demographic data

10.0 STATISTICAL CONSIDERATIONS

10.1 Study Design/Study Endpoints

This is a single-center Phase I/Ib study aiming to evaluate the safety, efficacy, and tolerability of nivolumab combined with therasphere, Y-90, in patients with advanced hepatocellular carcinoma.

The expected number of patients on dose escalation will be in the range of 9-15 based on the 3+3 design. Six patients will be treated at the MTD in the dose escalation phase. The dose calculation for Yttrium-90 Therasphere will be done according to standard protocol at Northwestern Memorial Hospital. Please note - details of this are located in section 8.1.

Phase Ib Expansion Cohort:

A Simon two stage optimum Phase II design (1989) will be used to test the null hypothesis that the response rate is 10% versus an alternative hypothesis of 30 [36]. Up to 29 evaluable patients will be entered into Phase 1b. The 6 patients at the MTD in Phase 1 will be counted as part of the 29 in Phase 1b. In the first stage, 10 patients will be entered. If none or 1 show a response, then consideration will be given to trial termination due to inactivity of the treatment. If 2 or more of 10 show a response, then an additional 19 patients will be added. If 5 or fewer of 29 show a response, then the trial will conclude that the response rate could be as low as 10%. If 6 or more respond, then the trial will conclude that the response rate is greater than 10%. This design has a 20% chance of falsely concluding the rate is 10% (Type II error = 20%), and a 5% chance of falsely concluding that the rate is greater than 10% (Type I error = 5%). There is a 74% chance that the trial will show 0 or 1 responses in the first stage if the true response rate is 10%.

For the total sample size, Phase 1 requires 9-15 patients, Phase 1b requires 29 patients in a two-stage optimum Simon design. The 6 at the MTD in Phase 1 are counted as part of the 29. This would require up to 15 in Phase 1, 23 new patients in Phase 1b for a total of 38 patients. Target accrual is 40 patients to account for potentially unevaluable patients.

Treatment duration:

Treatment will continue until disease progression (imaging done every 8 weeks), intolerable side effects, or patient withdraws consent or is removed from the study for any other reason.

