Objectives	
Primary Objective(s):
 
 • Phase I: To identify maximum tolerated dose (MTD) of nivolumab for combination treatment of nivolumab and Y-90 in patients with advanced hepatocellular carcinoma. • Phase Ib: To evaluate the proportion of patients with objective response rate (ORR) to the combination treatment of nivolumab with Y-90. 
Secondary Objective(s):
 
 • To evaluate the toxicities (according to the NCCN CTCAE v4.03) and tolerability of nivolumab and y-90 in patients with advanced hepatocellular carcinoma • To evaluate the proportion of patients alive and progression free at 24 weeks in the described population. • To evaluate the disease control rate for the combination of Y-90 and nivolumab at 24 weeks from starting nivolumab treatment. 
Exploratory Objective(s):
 
 • Intratumoral Assessment: Fresh biopsy or archived tissue will be used if available. PD-L1 protein on tumor cells and the expression levels of other markers of inflammatory/immune signature that may include but not be limited to PD-1, OX40, CD73, CD39, T cell immunoglobulin and TIM3, GITRL, CTLA-4, CD3, CD4, CD8, CD45RO, FOXP3, and granzyme by IHC and/or flow cytometry will be evaluated. Whole exome sequencing and computational analyses will be performed to assess mutanome and immunome (subpopulations of immune cells). • Circulating free DNA (cfDNA) mutation analyses: Blood will be drawn before treatment and every 8 weeks with imaging for the first 24 weeks then every 16 weeks until disease progression. Change in clonal burden landscape of various mutanome and immunome will be analyzed to investigate its correlation with treatment response or development of resistance to treatment.
Sample Size	Phase 1: 9-15 patients, Phase 1b requires 29 patients in a two-stage optimum Simon design. The 6 at the MTD in Phase 1 are counted as part of the 29. This would require up to 15 in Phase 1, 23 new patients in Phase 1b for a total of 38 patients. Target accrual is 40 patients to account for potentially unevaluable patients.
Diagnosis & Key Eligibility Criteria	Subjects with advanced hepatocellular carcinoma who are non-transplant candidates.

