4.3 Phase I Dose Escalation Scheme

In this phase 1/1b pilot study, the dose escalation component will be for nivolumab, starting at a dose of 80mg. Please see the table in statistical section for dose adjustments.

Phase I Dose Escalation Plan based on 3+3 design:

Dose Level	Nivolumab
1	80mg IV every 2 weeks
2	240mg IV every 2 weeks

NU Study Number: NU 16101
BMS Study Number: CA 209-615

A standard “3+3” dose escalation design will be utilized. Initially, 3 patients will be enrolled at the starting dose (level 1), after which enrollment will be temporarily suspended until all 3 patients complete the DLT evaluation period (defined as cycle 1 or the first 28 days of treatment). Once all 3 patients complete the DLT period and toxicity data has been submitted, the Data and Safety Monitoring Committee (DSMC) will review the data and confirm the presence or absence of any DLTs (defined below). The following rules will be used at each dose level to determine whether or not to proceed to the next dose level:

- If 0 of 3 patients at a given dose level experience a DLT (defined below), then escalation will proceed to the next dose level.
- If 2 or 3 of 3 patients at a given dose level experience a DLT, then one of the following must occur:
 - If this happens at level 1, the PI will discuss with DSMC and BMS to determine the necessary outcome.
 - If this happens at level 2 or beyond, the previous level will be declared the maximum tolerated dose (MTD).
- If 1 of 3 patients at a given dose level experiences a DLT, then an additional 3 slots will be added (for a total of 6 patients at that level):
 - If 1 of 6 total experiences a DLT, then escalation will proceed to the next level.
 - If ≥ 2 of 6 total experience a DLT, the previous level will be declared the MTD.

NOTE: Whichever dose level is declared the MTD must have 6 total patients treated at that level. For example, if 3 patients are treated at level 2 and 0 patients experience DLT, escalation would then proceed to level 3. However, if ≥ 2 patients at level 3 experience DLT, enrollment to level 2 would need to be re-opened to enroll an additional 3 patients at that level (with 0 or 1 DLT observed in 6 total patients) in order to declare level 2 the MTD.

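### The Phase I upper limit of 15 and the maximum total of 38 are each 3 too high: the two-level 3+3 rules in section 4.3 give at most 12 and 35

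*Combined protocol and SAP*

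**What the plan says.** Section 10.1 gives the Phase I size as follows: "The expected number of patients on dose escalation will be in the range of 9-15 based on the 3+3 design". The Statistical Methodology row of the Study Summary repeats that range, and the Sample Size row has "Phase 1: 9-15 patients, Phase 1b requires 29 patients in a two-stage optimum Simon design". Both section 10.1 and the Sample Size row count the 6 patients at the MTD among the 29, and build the total on the upper limit: "This would require up to 15 in Phase 1, 23 new patients in Phase 1b for a total of 38 patients". Then comes the allowance: "Target accrual is 40 patients to account for potentially unevaluable patients".

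Section 4.3 sets the rules that produce the Phase I count. Its table has two nivolumab levels. Each level opens with 3 patients. If 1 of the 3 has a DLT, "then an additional 3 slots will be added (for a total of 6 patients at that level". A note adds: "Whichever dose level is declared the MTD must have 6 total patients treated at that level". For 2 or 3 DLTs among the first 3 patients at the lowest level, the rule is "If this happens at level 1, the PI will discuss with DSMC and BMS to determine the necessary outcome".

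Section 3.0 caps enrolment at 40, divided into 15 for Phase I and 25 more for Phase Ib. Section 8.2.5 takes the study into Phase Ib only if 240 mg is the MTD.

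**The concern.** The text attributes the range to the 3+3 design, so it should follow from the rules in section 4.3. With two levels and no rule that places a seventh patient at either, the count cannot exceed 6 + 6. An upper limit of 15 would need a further cohort of 3 that section 4.3 does not define.

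The stakes are modest. The sample-size statement is the part of the plan that readers use to check accrual. Here it disagrees with the escalation rules it cites, and it understates the room left under the ceiling of 40 for patients who prove unevaluable or are replaced.

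**Working it through.** **The plan's own sum.** New Phase Ib patients: 29 − 6 = 23. Stated maximum: 15 + 23 = 38. Implied reserve: 40 − 38 = 2. The additions are correct, so the question is whether the input of 15 can arise.

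**Inputs from section 4.3.** Two levels; 3 patients at opening; expansion to 6; 6 required at the MTD; escalation on 0 of 3 or 1 of 6 DLTs; the level below becomes the MTD on 2 or more DLTs. Section 2.1.1 is also needed. It defines the MTD as the highest dose with DLTs in fewer than 2 of 6 patients. The escalation bullets alone send a tolerated level 2 on to a next level that is not in the table.

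**All paths (patients at level 1 + patients at level 2).**

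| Outcome | Count |
|---|---|
| MTD is level 2; level 1 had 0/3 | 3 + 6 = 9 |
| MTD is level 2; level 1 had 1/6 | 6 + 6 = 12 |
| MTD is level 1; level 2 failed in its first 3 | 6 + 3 = 9 |
| MTD is level 1; level 2 failed after 6 | 6 + 6 = 12 |
| No MTD; level 1 had 2 or 3 DLTs in 3 | 3 |
| No MTD; level 1 had 2 or more DLTs in 6, before level 2 | 6 |
| No MTD; level 1 re-opened after level 2 failed, then 2 or more DLTs in 6 | 6 + 3 = 9 or 6 + 6 = 12 |

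If level 2 starts at 0/3, is filled to 6 and then fails, it still holds only 6 patients and is covered by the rows above. When an MTD is declared the count is 9 or 12; over all paths it is 3, 6, 9 or 12. The stated 9 reproduces and the stated 15 does not.

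**Totals if 240 mg is the MTD.**
- Both Simon stages completed: 9 + 23 = 32 or 12 + 23 = 35.
- Stop after stage 1 ("In the first stage, 10 patients will be entered", 6 of them from Phase I, so 4 new): 9 + 4 = 13 or 12 + 4 = 16.
- Excess at the top: 15 − 12 = 3 and 38 − 35 = 3.
- Reserve at the maximum: 40 − 35 = 5, against 2.

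If 240 mg is not the MTD, section 8.2.5 does not carry the study into Phase Ib, and the total stays at 12 or fewer.

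**Simon design.** For at most 1 response in 10 and at most 5 in 29, exact binomial calculation gives a type I error of 0.047 at a 10% response rate, power of 0.805 at 30%, and a probability of early termination of 0.736 at 10%. These agree with the stated 5%, 20% type II error and 74%.

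**The case against.** The best defence is that 15 is an enrolment figure: 12 design slots plus room for replacements. Section 3.0 lends it some support. Its Phase Ib share of 25 equals 23 + 2, so the whole allowance of 2 sits in Phase Ib, and any Phase I replacement has to fit within the 15. Replacements are foreseen in sections 4.2.2 and 4.10 for patients who do not start nivolumab within 4 weeks of Y-90. A reader might infer that adding unevaluable patients afterwards (38 to 40) proves that 15 contains none. It does not, given the split in section 3.0. What defeats the defence in section 10.1 is the wording there: it derives the range from the 3+3 design and gives it as what Phase I needs. Neither section 10.1 nor section 3.0 mentions replacements within the 15.

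A second objection is that 12 is not a hard limit. This stands in part. A reader might infer that level-1 toxicity without a defined outcome can arise only early, after 3 or 6 patients. It can also arise after 9 or 12, when level 1 is re-opened and then has 2 or more DLTs in 6. One more cohort of 3 after 12 would make exactly 15. No document defines such a cohort, and none rules it out.

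Third, the note in section 4.3 works through an example with a level 3, so someone following it could count above 12. The example conflicts with the two-level table. It does not justify 15 either, because three levels under the same rules give 9, 12, 15 or 18 when an MTD is declared. For the same reason, the removal of a 480 mg level recorded in the summary of changes is at most a possible origin of the range. The point rests on the current text.

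Finally, the consequence is small. That is accepted.

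**Conclusion.** The point holds as a minor arithmetic inconsistency. Under the tabulated rules Phase I takes 9 or 12 patients when an MTD is declared and no more than 12 on any path. The upper limit of 15 and the maximum total of 38 are each 3 too high.

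The result rests on three assumptions: the two-level table governs rather than the level 3 example; the level-1 branch without a defined outcome adds no cohort; and the counts are of patients filling 3+3 slots, with replacements extra. The total of 35 also requires that 240 mg is the MTD and that both Simon stages are completed.

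A reader might go further and conclude that the trial is mis-sized or that the ceiling of 40 must come down. The documents do not support that. The error overstates need, the Simon operating characteristics reproduce, and a ceiling may reasonably hold a larger reserve.

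**What to change.** - Section 10.1 and both Study Summary rows: give Phase I as 9-12 patients under the tabulated 3+3 rules, noting that no further cohort is assumed where level-1 toxicity has no defined outcome.
- Section 10.1 and the Sample Size row: give the maximum total as 12 + 23 = 35 if 240 mg is the MTD and both Simon stages are completed. Keep 40, and state that it leaves 5 places at that maximum for unevaluable or replaced patients.
- Section 3.0: either say that the 15 is an enrolment cap that includes replacements, or align it with the new figures.
- Section 4.3: reconcile the level 3 example in the note with the two-level table.

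The cost is a few edited sentences. The Simon rules, the analyses, the 29 evaluable patients and the accrual ceiling are untouched.

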10.2 Data Analyses Plans

Any subject who has received the investigational combination will be analyzed in an intention to treat format. The MTD will be determined as described in Section 4.3. Objective response rate (ORR = CR + PR) as defined in Section 6.3.3.1 and disease control rate (CR+PR+SD) will be calculated and a 95% confidence interval for response will be obtained using the methods of Porcher and Desseaux (2012) [37]. Progression-free survival will be summarized using the Kaplan-Meier product limit curve. Besides the required reporting of adverse events, adverse events will be summarized for all patients in the trial by type, duration, severity, timing and attribution (probable cause of adverse event). Whole exome sequencing and computational analyses will be performed to assess mutanome and immunome (subpopulations of immune cells). Change in clonal burden landscape of various mutanome and immunome will be analyzed to investigate its correlation with treatment response or development of resistance to treatment.

11.0 STUDY MANAGEMENT

11.1 Institutional Review Board (IRB) Approval and Consent

It is expected that the IRB will have the proper representation and function in accordance with federally mandated regulations. The IRB should approve the consent form and protocol.

In obtaining and documenting informed consent, the investigator should comply with the applicable regulatory requirement(s), and should adhere to Good Clinical Practice (GCP) and to ethical principles that have their origin in the Declaration of Helsinki.

Before recruitment and enrollment onto this study, the patient will be given a full explanation of the study and will be given the opportunity to review the consent form. Each consent form must include all the relevant elements currently required by the FDA Regulations and local or state regulations. Once this essential information has been provided to the patient and the investigator is assured that the patient understands the implications of participating in the study, the patient will be asked to give consent to participate in the study by signing an IRB approved consent form.

Prior to a patient's participation in the trial, the written informed consent form should be signed and personally dated by the patient and by the person who conducted the informed consent discussion.

11.2 Subject Recruitment and Screening

Subjects will be recruited through hepatology clinic, hepatocellular carcinoma clinic, pre-transplant clinic and medical oncology clinics. They will be identified by the PI, or referred to the PI from other hepatologists, transplant surgeons or medical oncologists. The PI or sub-investigator will discuss the protocol with potential subjects (patients from one of the above clinics) that may qualify for the study based on the inclusion/exclusion criteria in this protocol. If the patient is interested they will discuss the study in depth and if they prefer, they can take home information (combination consent/HIPAA form) on the study to discuss with their family/significant other/primary care provider.

Once a potential subject decides they'd like to participate in the study they will come in to meet with the research coordinator/PI and/or sub-I to sign the consent after any other questions are answered. It is only after the informed consent is signed that any study-related procedures can be performed. The subject will be given a signed copy of the informed consent and the consent process will be documented in the subject's medical record.

11.3 Amendments

The Principal Investigator will formally initiate all amendments to the protocol and/or informed consent. All amendments will be subject to the review and approval of the appropriate local, institutional, and governmental regulatory bodies, as well as by Bristol-Meyers Squibb. Amendments will be distributed by the lead institution (Northwestern) to all affiliate sites upon approval by the Northwestern University IRB.

11.4 Registration Procedures

For potential patients, study teams are asked to inform the QAM of the date and time that the patient will need to be registered ([contact]).

BEFORE a patient can be treated on study, please complete and submit the following items to confirm eligibility and receive an identification number:

- Patient's signed and dated informed consent form (upload to NOTIS and keep original hard copy in a secure location/study chart)
- Eligibility checklist (signed and dated by the treating physician – upload to NOTIS)
- Eligibility eCRF (complete in NOTIS)
- Copy of the pathology report (upload to NOTIS)

The QAM will review all source documentation required to confirm eligibility that is readily available in the patient's electronic medical record (EMR). Any information that is not available in the EMR must be de-identified and emailed to the QAM. Once the QAM confirms the patient is eligible, he or she will register the patient, assign a subject identification number, provide a cohort assignment, and send a confirmation of registration to involved personnel. Registration will then be complete and the patient may begin study treatment.

11.5 Data Submission

Once a subject is confirmed and registered to the study, eCRFs should be submitted according to the detailed data submission guidelines (provided in a separate document). Generally, all data for phase I patients during the time period patients are evaluated for Dose Limiting Toxicities (DLTs) must be submitted on a weekly basis.

11.6 Instructions for Participating Sites

Before the study can be initiated at any site, the following documentation must be provided to the Clinical Research Office at Northwestern University:

- Signed and completed Letter of Invitation to participate in the study.
- Signed copy of Northwestern University's Data Monitoring Committee policy pertaining to data submission.
- Draft informed consent form should for review/approval prior to submission to the local IRB
- A copy of the official IRB approval letter for the protocol and informed consent.
- CVs and medical licensure for the local PI and any sub-investigators who will be involved in the study at the site.
- Form FDA 1572 appropriately filled out and signed with appropriate documentation.

Additional activities may be required prior to site activation (i.e. contract execution, study-specific training). Full requirements will be outlined in a memo upon receipt of the signed Letter of Invitation.

11.7 Data Management and Monitoring/Auditing

This study will be conducted in compliance with the Data Safety Monitoring Plan (DSMP) of the Robert H. Lurie Comprehensive Cancer Center of Northwestern University (please refer to Appendices for additional information). The level of risk attributed to this study requires High Intensity Monitoring as outlined in the [DSMP](#). The assigned QAM, with oversight from the Data Monitoring Committee, will monitor this study in accordance with the study phase and risk level. Please refer to study-specific data submission guidelines.

11.8 Adherence to the Protocol

Except for an emergency situation in which proper care for the protection, safety, and well-being of the study patient requires alternative treatment, the study shall be conducted exactly as described in the approved protocol.

11.8.1 Emergency Modifications

Investigators may implement a deviation from, or a change of, the protocol to eliminate an immediate hazard(s) to trial subjects without prior IRB approval.

For any such emergency modification implemented, an IRB modification form must be completed within 5 business days of making the change, and the QAM must be notified within 24 hours of such change.

11.8.2 Other Protocol Deviations

All other deviations from the protocol must be reported to the assigned QAM using the appropriate form.

A protocol deviation is any unplanned variance from an IRB approved protocol that:

- Is generally noted or recognized after it occurs.
- Has no substantive effect on the risks to research participants.
- Has no substantive effect on the scientific integrity of the research plan or the value of the data collected.
- Did not result from willful or knowing misconduct on the part of the investigator(s).

A protocol deviation may be considered an instance of Promptly Reportable Non-Compliance (PRNC) if it:

- Has harmed or increased the risk of harm to one or more research participants.
- Has damaged the scientific integrity of the data collected for the study.
- Results from willful or knowing misconduct on the part of the investigator(s).
- Demonstrates serious or continuing noncompliance with federal regulations, State laws, or University policies.

